8.3 Treatment of adverse events

8.3.1 Observe and record

Researchers should ask patients to truthfully report the changes in their condition after acupuncture and avoid induced questions.

Any adverse reaction during the test should be filled in the "Adverse Event Form", followed up and investigated, and the treatment process and results should be recorded in detail until the laboratory examination returns to normal and the symptoms and signs disappear. Follow-up and follow-up methods can choose hospitalization, outpatient clinic, home visit, telephone, communication, etc. according to the severity of adverse reactions.

8.3.2 Medical treatment

When an adverse reaction is discovered, the researcher decides on diagnosis and treatment measures based on the condition and decides whether to suspend the observation. In the event of a serious adverse event, the study immediately took necessary measures to protect the safety of the subjects.

8.3.3 Report

For all adverse events that occurred during the clinical study period (including washout period, observation period, routine treatment period, and follow-up period, a total of at least 10 weeks), the investigator must truthfully fill in the "Adverse Events/Adverse Reaction Record Form" and include it on the report Sign and date. If a serious adverse event (SAE) occurs, it will be handled as usual, regardless of whether it is related to the treatment of this study, it must be reported to the head of the PHN clinical trial group

of Jiangsu Provincial Hospital of Traditional Chinese Medicine within 24 hours of the investigator's knowledge (contact/Tel: [name] /[name], Email: [contact]), and report to the ethics committee; if the enrolled patient is pregnant, it is also regarded as a major event, and the adverse event/adverse reaction record form must be filled in, and the investigator is informed Report to the person in charge of the PHN clinical trial group of Jiangsu Provincial Hospital of Traditional Chinese Medicine within hours (contact person/telephone: [name]/[name], email: [contact]), and report to the ethics committee at the same time.

9. Quality control and assurance of the study

9.1 Clinical quality control measures

Establish standard operating procedures and quality control procedures for experimental observation indicators. The test results must be printed on a computer, and the data should be traceable.

9.2 Pre-clinical trial training

In order to ensure the smooth progress of the research, the research team must hold a special clinical training meeting to conduct unified training for clinical researchers before the official launch of the clinical trial.

Carry out key training on the project implementation plan and various standard operation procedures (Standard Operation Procedure, SOP), so that each clinical researcher (including acupuncture operators, scale evaluators, research nurses, quality controllers and other related research Personnel) To be familiar with the research process and specific test implementation rules to improve the consistency of internal observations by researchers and the consistency between observers, and to ensure the reliability of clinical research conclusions.

Sign the investigator's statement and establish indicator observation and quality control SOPs in the participating hospitals.

9.3 Measures to improve subject compliance

In order to obtain better compliance, make the final summary analysis not less than 80% of the total number of cases entered into the trial, adopt the following measures to improve patient compliance: adhere to the principle of voluntariness, sign patient informed consent; from medical treatment Improve and maintain good patient compliance in terms of quality, treatment environment, medical expenses, etc., to encourage patients to adhere to treatment as much as possible during the study period; pay attention to establishing a good doctor-patient relationship, and explain in detail various examinations, treatments and re-examinations for included cases To obtain the patient's consent and cooperation for the purpose and necessity; record their contact information in detail for follow-up.

9.4 Quality control and quality assurance system

Operators in charge of acupuncture treatment in each center must have an acupuncturist qualification certificate and independently undertake clinical treatment for more than 2 years. Scale assessors and other investigators participating in the trial should perform their respective duties, strictly follow the clinical trial protocol, and adopt standard operating procedures to ensure the implementation of the clinical trial quality control and quality assurance system.

10. Data collection, management, monitoring and auditing

The data collection and analysis, quality assurance, trial conduct and implementation for this study will follow Good Clinical Practice (GCP) guidelines43. Before the AEEPN trial is officially initiated, the research group will hold a specialized clinical training meeting to conduct unified interpretation and training of all clinical researchers on the study implementation scheme, standard operation procedure (SOP), CRF filling, EDC system use and electronic data entry, so that researchers in each clinical center (including acupuncturists, outcome assessors, data recorders, data entry clerks, research nurses, quality controllers and other related researchers) will be familiar with the study protocol and SOP, thereby the internal observation consistency of researchers will be improved.

All CRFs for each participant will be filled in timely by researchers in each clinical center, including assessment scales, questionnaires, treatment compliance, concomitant medication and rescue medication use, AE, etc.. Any evidence-based correction of CRF, only lines can be drawn. The marginal note modified data will be signed and dated by the researcher, and the original records shall not be erased or overwritten. All original documents and CRFs will be stored in the clinical study office. Besides, all data will be accurately double-entered into EDC system and the electronic CRF are identical to paper CRF. Once the data entry is completed, the database will automatically perform consistency checks, missing value checks, value range and logic checks. If any inconsistencies or missing data are found, the data will be re-checked and corrected based on the original documents and CRFs. And the contents, time and operators of all operations will be recorded by the EDC system to ensure the accuracy, completeness and traceability of the research data entry. When 50% of the participants' data is entered into the EDC system, we will perform an interim analysis on the primary outcome, whichever comes first. This will be performed by an independent statistician and will inform us whether the intervention has been proved to be effective (beyond reasonable doubt). Subsequently, we will decide whether (if necessary) to modify the study or terminate it prematurely. When all data is entered in the EDC system, 10% of the eCRF will be randomly selected for manual inspection, and the database will be locked and sent to the statisticians for further statistical analysis after all data inspection is completed and updated. Finally, we will submit the end of trial notification and final report to the Ethics Committees of 7 clinical centers, the Sponsor and ClinicalTrials.gov.

11. Statistical Analysis

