3.4 Sample size

According to previous studies, it is anticipated that a difference in primary outcome (NRS-11) between EA group and SEA group is 1.2 and the combined standard deviation of the two groups is 3.5. To achieve 90% statistical power and control the type I error rate below 0.05, we calculated by PASS 15 that a sample of 448 participants (224 participants in each group) will be required to detect a two-sided significant difference between the two groups and compensate for a dropout rate of 20%. All participants are equally distributed among 7 clinical centers, and 64 participants per center will be recruited.

4. Subjects

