11.5 Statistical analysis method

The description of the enumeration data will use the number of cases and percentages, and the comparison between groups will use chi-square test, Fisher's exact probability method, Wilcoxon rank sum test, CMH χ^2 test, and WLS covariance. The description of the measurement data will be carried out using the mean \pm standard deviation, median, maximum, and minimum value. Quantitative data conform to a normal distribution with t test (test for homogeneity of variance between groups, with 0.05 as the test level, uneven variance The Satterthwaite method was used for the corrected t test), the Wilcoxon rank sum test and the Wilcoxon signed rank sum test were used for non-normal distribution. The hypothesis test uses a two-sided test uniformly, and the test statistics and the corresponding P value are given. P<0.05 is considered statistically significant, and P<0.01 is considered highly statistically significant.

12. Ethical considerations

Ethical review: This study will follow the relevant regulations of the World Medical Congress "Declaration of Helsinki". Before the start of the study, the clinical study was carried out after the ethics committee approved the trial protocol. If this protocol is revised during the implementation of the clinical trial, it will be submitted to the ethics committee for approval before implementation.

Benefits and risks: The subjects and the society will benefit from this research, including the pain of the subjects will be improved, and the subjects can get the research-related inspection fees and registration fees for free during the research period. Obtain good medical services during the period. At the same time, this study may help more patients in the international community recognize the analgesic effect of electroacupuncture on PHN patients, so as to help other patients with the same disease get rid of pain as soon as possible. Subjects are at risk of possible adverse events due

to acupuncture during the experiment, such as fainting needles, broken needles, local infections or subcutaneous hematomas, etc. Researchers will take corresponding diagnosis and treatment measures according to the condition, and suspend observation when necessary to protect Subject safety.

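### Section 10 allows stopping for efficacy at the halfway look without a numerical boundary, while Sections 3.4 and 11.5 promise type I error below 0.05 with an unadjusted final P<0.05

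*Protocol*

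**What the plan says.** Three parts of the protocol bear on this.

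- **Section 10 (data collection, management, monitoring and auditing).** Once half of the participants' data have been entered, "we will perform an interim analysis on the primary outcome". An independent statistician performs it, and the result "will inform us whether the intervention has been proved to be effective (beyond reasonable doubt"). Then "we will decide whether (if necessary) to modify the study or terminate it prematurely". There is no significance level, boundary or spending function, and no limit on what may be modified.
- **Section 3.4 (sample size).** The design assumes a difference of 1.2 on the NRS-11, a standard deviation of 3.5 and 20% dropout. It aims "To achieve 90% statistical power and control the type I error rate below 0.05", and arrives at 448 participants (224 per group). The interim look is not mentioned.
- **Section 11.5 (statistical analysis method).** "The hypothesis test uses a two-sided test uniformly", and "P<0.05 is considered statistically significant, and P<0.01 is considered highly statistically significant". The 0.01 level is only a label for stronger evidence, so 0.05 is the sole decision threshold. The interim look is not mentioned here either.

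**The concern.** A look that can end the trial because the treatment appears effective gives a false positive a second chance to occur. To keep the overall error at 5%, the final test must give up some of its 0.05 in exchange for what the interim test can spend. Section 11.5 gives nothing up, Section 3.4 leaves nothing in reserve, and the interim criterion in Section 10 is verbal and cannot be turned into a probability.

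The type I error of the confirmatory test and the decision to end the trial are both at stake. A boundary chosen after the interim result is known could not be shown to control the error, so this has to be settled beforehand. The open option to modify the study raises the same problem in a form that cannot be calculated, because no limits are set on it.

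**Working it through.** **Inputs.** Difference 1.2, SD 3.5, two-sided 0.05, power 90%, dropout 20% (Section 3.4); 1:1 allocation (Section 3.2); one look at 50% (Section 10); final threshold P<0.05, two-sided (Section 11.5). The interim threshold is not stated, so it is varied.

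**Step 1: reproduce the plan's sample size.**

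n per group = 2 × (SD/difference)² × (z₀.₉₇₅ + z₀.₉₀)² = 2 × (3.5/1.2)² × (1.960 + 1.2816)² = 178.8, rounded up to 179.

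With dropout: 179/0.8 = 223.75, rounded up to 224 per group, 448 in total.

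This is the protocol's figure exactly. It is a single-analysis design using the full 0.05, with no error reserved for an interim test. (A noncentral-t calculation gives 180 and then 225 per group, which does not change the point.)

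**Step 2: overall type I error with the final test at 0.05.** Under the null hypothesis the interim and final statistics Z₁ and Z₂ are bivariate standard normal with correlation √0.5 when the look is at half the information. Let c₁ be the critical value for the interim P-value.

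- Two-sided stop: 1 − P(|Z₁| ≤ c₁ and |Z₂| ≤ 1.960)
- Stop for benefit only: P(Z₁ > c₁ or |Z₂| > 1.960)

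| Interim threshold | c₁ | Two-sided stop | Benefit-only stop |
|---|---|---|---|
| P<0.001 | 3.291 | 5.02% | 5.01% |
| P<0.005 | 2.807 | 5.19% | 5.09% |
| P<0.01 | 2.576 | 5.46% | 5.23% |
| P<0.05 | 1.960 | 8.31% | 6.66% |

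Every entry is above 5%.

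**Step 3: sensitivity to timing.** With correlation √0.4 or √0.6 (a look at 40% or 60% of the information), the two-sided P<0.05 case is 8.63% or 7.96%, and the P<0.001 case is 5.04% or 5.01%. The threshold matters far more than the exact timing.

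**Step 4: final threshold that restores 5%.** Solving 1 − P(|Z₁| ≤ c₁ and |Z₂| ≤ c₂) = 0.05 for c₂ at half the information:

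- interim P<0.001: final P<0.0498 (Haybittle-Peto)
- interim P<0.0052: final P<0.0480 (O'Brien-Fleming, critical values 2.797 and 1.977)
- interim P<0.01: final P<0.0452
- interim P<0.05, two-sided: no solution, because the interim test alone spends the full 5%

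**Step 5: power after the correction.** With 179 evaluable per group, the expected final statistic is 1.2/(3.5 × √(2/179)) = 3.24, and the expected interim statistic is 3.24 × √0.5. Power is 90.0% for the fixed design, 89.8% with O'Brien-Fleming and 90.0% with Haybittle-Peto.

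**The case against.** The strongest reply is that numerical boundaries are often left to a statistical analysis plan or an interim analysis plan, and neither is available here. On this view Section 11.5 is a general convention for all tests, and the error limit in Section 3.4 is the overall level that any later boundary must respect. In addition, proof beyond reasonable doubt suggests a very strict criterion, and a question about whether the treatment works suggests stopping only for benefit. On that reading the overall error is about 5.01%, and the correction moves the final threshold only from 0.05 to 0.0498.

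Part of this stands. The missing boundary alone would not be enough for a finding, the 8.3% is the unfavourable end of a range and not an estimate, and under a strict rule the excess is trivial.

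The rest does not remove the contradiction. The protocol does more than defer the matter: it fixes 0.05 for every test, without exception for the primary one. A later plan that held 5% overall while allowing an efficacy stop would need a final threshold below 0.05, and so would have to depart from Section 11.5. The strict reading of the interim criterion is plausible, but nothing in the text secures it, and the only significance threshold the protocol prints is 0.05.

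**Conclusion.** The point holds. As written, the efficacy stop in Section 10, the unadjusted threshold in Section 11.5 and the error limit in Section 3.4 are incompatible. The overall type I error lies between about 5.0% and 8.3%, and the protocol gives no means of saying where.

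The range assumes one look at half the information, approximately normal test statistics, a final two-sided test at 0.05, and interim thresholds from 0.001 to 0.05. It leaves out any effect of modifying the study after the look. The correction should be made before any interim data are seen. Confidence is high that the passages conflict; how much inflation would occur in practice is unknown.

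**What to change.** State one group-sequential rule in Section 10, carry the matching final threshold into Section 11.5, and name the look in Section 3.4. Suggested wording:

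> One interim analysis of the primary outcome is done at 50% information. The trial may stop for efficacy only if two-sided p<0.0052; otherwise the final primary test is at two-sided p<0.0480 (O'Brien-Fleming).

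Haybittle-Peto (interim p<0.001, final p<0.0498) serves equally well, as does dropping the efficacy look and keeping 0.05. The choice is the sponsor's.

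Three related points belong in the same edit:

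- **Trigger.** Define it by participants with a week-4 NRS-11 value, not by data entered. With 2 × 179 = 358 evaluable participants planned, half is 179. The phrase about whichever comes first has only one trigger and should go. The O'Brien-Fleming pair is exact only at half the information: by the Step 2 formula it gives 5.06% at 40% and 4.94% at 60%.
- **Reporting.** Say that the independent statistician returns only a recommendation to continue or stop.
- **Modification.** Remove the open option to modify the study on the basis of the interim effect, or at least list which changes are allowed.

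The cost is protocol wording and at most 0.2 percentage points of power (90.0% to 89.8%), with no extra patients. The change addresses type I error only: an effect estimate from an early stop remains biased upward under either boundary.

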3.2 Randomization

Eligible patients are randomly allocated in a ratio of 1:1 to the EA or SEA group by a central randomization system (Clinical Research Data Collection and Management System of Jiangsu Province Hospital of Chinese Medicine). Multi-center stratified variable block randomization is used, and the block size of each center is randomly set to 4, 6, and 8. Considering that the number of patients in each stratum fluctuates due to block variation, 21 stratums are preset at random and take the first 7 groups with the number of patients equal to 64 as the final grouping. The randomization sequence is

generated and validated by an independent statistician using R software, and then imported into EDC's central randomization system and kept by an administrator who do not participate in this trial. The central randomization system has set strict personnel permissions, and no one has right to view the randomization scheme except the highestlevel system administrator. After participants meet all the inclusion criteria and complete the baseline assessment, an acupuncturist will log in to the central randomization system to apply for random numbers which will be displayed then, and the patients will receive the corresponding treatment. The Clinical Research Coordinators (CRCs) will be responsible for enrolling participants, obtaining informed consent, and CRF recording.

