3.3 Blinding

Patients and CRCs (i.e., outcome assessors, data recorders, data entry clerks and statistical analysts) are blinded to the group assignment. Due to the nature of the intervention, acupuncturists are not be blinded to the treatment.

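### Section 10 gives the interim efficacy verdict to the group running the trial and lets that group modify the study knowing it, with no limit on who sees the result or what may change

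*Protocol*

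**What the plan says.** The interim analysis is described in the protocol, Section 10 (Data collection, management, monitoring and auditing). It concerns the primary outcome, is triggered when half of the participants' data are in the EDC system, and is done by an independent statistician. The result "will inform us whether the intervention has been proved to be effective (beyond reasonable doubt"). The next sentence gives the decision to the same first person: "Subsequently, we will decide whether (if necessary) to modify the study or terminate it prematurely".

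Four other places bear on this:

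- Section 3.2 restricts access to the allocation list: "no one has right to view the randomization scheme except the highestlevel system administrator".
- Section 3.3 blinds patients, outcome assessors, data staff and statistical analysts to group assignment, and states that "acupuncturists are not be blinded to the treatment".
- Section 4.6 has the statistician and the main researcher judge, before the analysis, which cases to eliminate.
- Section 12 sends any protocol revision to the ethics committee before it takes effect.

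The protocol names no data monitoring committee or other independent decision body. It does not restrict circulation of the interim result and does not list the permitted modifications.

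**The concern.** An independent statistician protects the calculation. What happens to the result afterwards is left to the trial group, which both hears whether electroacupuncture has been shown to work and may change a running trial in response. If the sample size, eligibility, outcome definition or analysis is altered after that, nobody can show afterwards that the change was independent of the result. The same holds for discretionary calls that need no amendment, such as case elimination.

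This matters more here than in a trial with an objective endpoint. The primary outcome is a patient-reported 0 to 10 pain score, treatment is 20 face-to-face sessions, and the person giving it knows the allocation. The problem concerns who learns the result and who acts on it, so it would remain under any stopping boundary.

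**Working it through.** No figure in the protocol decides this point. The check is a reading of the passages together, plus the arithmetic that limits how many participants could be affected.

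**1. Who the first person is.** Section 10 does not define it. Later in the same paragraph the same first person submits the end-of-trial notice and the final report to the ethics committees, the Sponsor and ClinicalTrials.gov. It is therefore distinct from the Sponsor and from the independent statistician. Section 1 attributes the trial to a research group in the first person. The natural reading is the group that runs the trial.

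**2. What that group receives and may do.**

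| Step | Section 10 | Limit stated in the protocol |
|---|---|---|
| Computes the comparison | independent statistician | independence |
| Receives the efficacy verdict | trial group | none |
| Decides on modifying or ending the trial | trial group | ethics approval of revisions (Section 12) |
| Scope of modification | open | none |

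**3. What discretion remains afterwards.** Section 4.6 leaves case elimination to a joint judgement by the statistician and the main researcher. Section 11.1 analyses the main variables in both the full analysis set and the per-protocol set, and the other efficacy measures in the per-protocol set. Eliminations therefore feed into the reported results. Nothing in the protocol prevents the main researcher from knowing the interim verdict when making them.

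**4. The planning figure.** Section 3.4 assumes that "a difference in primary outcome (NRS-11) between EA group and SEA group is 1.2" and that "the combined standard deviation of the two groups is 3.5", with 90% power, two-sided alpha of 0.05 and 20% dropout.

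- Evaluable per arm: n = 2 × (1.960 + 1.2816)² × (3.5/1.2)² = 2 × 10.51 × 8.507 ≈ 178.8, so 179.
- Randomised per arm: 179 / 0.8 = 223.75, so 224, and 448 in total.

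The stated sample size reproduces, so it is not in question.

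**5. How many participants could be affected.** Half of 448 is 224. That is an upper limit. The trigger is data entered, not participants enrolled. Treatment takes 4 weeks, follow-up another month, and data are double-entered. By the time half of the data are in, more than half of the participants will probably have been randomised, and some of those may already have given their week 4 score.

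**6. How large a bias could be.** This cannot be derived. It would need the size and the direction of any shift in the between-arm difference caused by knowing the verdict, and the protocol gives neither.

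**The case against.** Several objections have force.

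- *Concealment and blinding are intact.* A reader might infer that releasing the verdict undoes Sections 3.2 and 3.3. It does not. Those sections protect individual allocations, and a trial-level verdict reveals no participant's group. Acupuncturists know the allocations they deliver whatever the interim shows.
- *The recipients are inferred.* A reader might also infer that acupuncturists or assessors will be told. Section 10 itself distinguishes the research group, which holds the training, from the researchers at each centre. Nothing says that the verdict is passed to the centres. What stands is that nothing prevents it.
- *The verdict says little.* No estimate, P value or arm summary is mentioned. A verdict of not proved rules out only a strong result. Conversely, for an efficacy look, a bare recommendation to continue tells the group nearly the same thing. This is correct, so the main gain from a change is to remove redesign on comparative results, with only a modest gain in secrecy.
- *A false-positive rate can be attached.* One could assume a shift favouring electroacupuncture after the interim and compute an inflated type I error. The documents support neither its size nor its sign. If there were truly no effect, a two-sided interim boundary at or below 0.05 would declare electroacupuncture superior in at most 0.05/2 = 2.5% of trials. In nearly all others the group would hear not proved, which is unlikely to encourage staff. If the verdict were proved, early termination is an explicit option and there may be no second part to bias.
- *Ethics review exists.* Section 12 means that the group cannot revise the protocol alone. That is a real check on the change, but it does not make the people who propose it unaware of the result.
- *The detail may be elsewhere.* Interim procedures are often set out in a SAP, which is not shown here. Silence would then be no finding. Here, however, the protocol itself names the trial group as recipient and gives it the decision to modify.

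**Conclusion.** The point holds in a limited form. As written, Section 10 lets the group that hears the efficacy verdict decide whether to modify the trial, with no stated limit on circulation or on what may change. A later design change, or a case elimination under Section 4.6, could be challenged as result-driven, and ethics review would not answer that challenge.

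It does not follow that allocation concealment or blinding fails, that treating staff will learn the result, or that exactly half of the trial is exposed. About 224 of 448 is the most that can be said, and fewer is likely. No inflation of the type I error should be quoted, because none follows from the documents.

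The conclusion assumes that the first person in Section 10 means the trial group, which is the natural reading but an inference. It warrants a wording change because that change is cheap and removes an avoidable line of attack on the result.

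**What to change.** Replace the two sentences in Section 10 on reporting and deciding with:

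> The independent statistician applies the interim stopping rule fixed before the interim data are seen and returns only a recommendation to continue or stop. No estimate, P value or arm-level efficacy summary is released to investigators, acupuncturists, CRCs or the trial's analysts before database lock. If the trial continues, the primary outcome, sample size, eligibility criteria and analysis are not changed on the basis of comparative interim efficacy results. Changes prompted by safety or external evidence remain possible, are documented as such and go to the ethics committee.

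The wording works only if the stopping rule is stated. This protocol does not give one, so it should be added here or the document that contains it should be cited.

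Cost: one paragraph plus the statement of the rule, and no extra staff, because the independent statistician is already planned. The trial group gives up the option of redesigning the study on comparative interim efficacy results. A recommendation to continue will still tell it that the stopping rule was not met.
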